10.1.2 Definitions for Efficacy Endpoints

Complete Remission Rate (CR + CRi)

Complete response rate, complete remission (CR) or complete remission with incomplete marrow recovery (CRi), will be defined as the proportion of subjects who achieved per the 2008 Modified IWCLL NCI-WG criteria as assessed by investigator using the best response at any time during the study. In addition, the 95% confidence interval for complete response rate (CR) rate based on the binomial distribution (Clopper-Pearson exact method) will be provided. Subjects who do not achieve a CR or CRi will be considered to be non-responders in the calculation of complete response rate.

Overall Response Rate (ORR)

ORR (CR + CRi + nPR + PR) will be defined as the proportion of subjects who achieved complete remission (CR), complete remission with incomplete marrow recovery (CRi), nodular partial remission (nPR), or confirmed partial remission (PR) based on the 2008 Modified IWCLL NCI-WG criteria as assessed by investigator using the best response at any time during the study. The corresponding exact 95% confidence interval for the proportion (Clopper-Pearson exact method) will be constructed. Subjects who do not respond will be considered non-responders.

Duration or Response (DOR)

The DOR for a given subject will be defined as the number of days from the day the criteria are met for CR, CRi, nPR, or PR (whichever is recorded first) to the earliest date that progressive disease (PD) is objectively documented (radiographic or clinical) or death

(i.e., DoR = PD/death/censoring date – earliest CR/CRi/nPR/PR date + 1 day). For subjects who have a PR before CR, CRi, or nPR in subsequent visits, the DOR is computed from the earliest PR. If a subject is still responding then the subject's data will be censored at the date of the last available disease evaluation or at the cut-off date for the interim analysis if the subject has a disease evaluation that is after the cut-off date. Only subjects with the iWCLL response criteria will be included in the analysis of DOR. The distribution of the duration of overall response will be estimated using the Kaplan-Meier methodology. Median duration of response will be calculated and the corresponding 95% confidence interval will be presented.

Time to Progression (TTP)

Time to progression for a given subject will be defined as the number of days from the date the subject started venetoclax to the date of earliest PD (radiographic or clinical) (i.e., TTP = PD/censoring date – first dose date + 1 day). All PD will be included regardless of whether the event occurred while the subject was taking venetoclax or had previously discontinued venetoclax. If the subject does not experience PD, then the subject's data will be censored at the date of the last available disease evaluation or at the cut-off date for the interim analysis if the subject has a disease evaluation that is after the cut-off date. If a subject does not have any post baseline disease assessments, the data will be censored at the first dose date plus 1 day. The distribution of the time to progression will be estimated using Kaplan-Meier methodology. Median time to progression and the corresponding 95% confidence interval will be estimated.

Progression Free Survival (PFS)

Progression-free survival (PFS) will be defined as the number of days from the date of first dose of venetoclax to the date of earliest PD (radiographic or clinical) or death (i.e., PFS = PD/death/censoring date – first dose date + 1 day). All disease progression will be included regardless of whether the event occurred while the subject was taking venetoclax or had previously discontinued the study drug. If the subject does not experience disease progression or death, then the subject's data will be censored at the

date of the last available disease evaluation, last known alive date, or at the cut-off date for the interim analysis if the subjects has a disease evaluation or death that is after the cut-off date. If a subject does not have any post baseline tumor assessment or clinical assessment for progression, the data will be censored at the date of first dose plus 1 day. Progression-free survival will be analyzed by Kaplan-Meier methodology. Median duration of PFS will be calculated and 95% confidence interval for median duration of PFS will be presented.

Overall Survival (OS)

Overall survival (time to death) for a given subject will be defined as the number of days from the date the subject started venetoclax to the date of the subject's death (i.e., $OS = \text{death/censoring date} - \text{first dose date} + 1 \text{ day}$). All events of death will be included, regardless of whether the event occurred while the subject was still taking venetoclax, or after the subject discontinued venetoclax. If a subject has not died, then the data will be censored at the date of the last study visit, the last contact date, the date the subject was last known to be alive, or at the cut-off date for the interim analysis if the subject has a death that is after the cut-off date. The date of the last study visit will be determined by selecting the last available date of the following study procedures for a subject: tumor assessment, clinical disease progression, physical examination, vital signs assessment, clinical laboratory collection, study drug, adverse event and concomitant medication assessment, performance status, quality of life evaluation, survival form, and drug and study completion form. The distribution of the time to death will be estimated using Kaplan-Meier methodology. Median survival time and the corresponding 95% confidence interval will be estimated.

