5.2.3 Prior and Concomitant Therapy

Any medication or vaccine (including over-the-counter or prescription medicines, vitamins and/or herbal supplements) that the subject is receiving at the time of enrollment, or receives during the study, must be recorded along with the reason for use, date(s) of administration including start and end dates, and dosage information including dose, route and frequency.

The AbbVie TA MD should be contacted if there are any questions regarding concomitant or prior therapy(ies).

Subjects should receive full supportive care during study participation, including hematopoietic growth factors, transfusion of blood products, fluid and electrolyte replacement, and antibiotics when appropriate. Subjects who use oral contraceptives, hormone-replacement therapy, or other maintenance therapy should continue their use.

Steroid therapy for anti-neoplastic intent will not be allowed either during or within 7 days prior to the first dose of venetoclax.

Inhaled steroids for the treatment of asthma or COPD, topical steroids, replacement corticosteroid therapy for an inherited or acquired deficiency are allowed.

In addition, limited corticosteroid treatment is allowed while on study for significant active autoimmune cytopenias, e.g., autoimmune hemolytic anemia (AIHA) or immune thrombocytopenia (ITP). IVIG (intravenous immune globulin) is also allowable.

For additional guidance regarding medications for management of neutropenia, refer to Section [6.1.9.3](#).

The AbbVie TA MD identified in Section [6.1.5](#) should be contacted if there are any questions regarding concomitant or prior therapy(ies).

General guidelines regarding excluded, cautionary and allowed medications are summarized in [Table 1](#) and [Table 2](#) below.

Subjects may not consume grapefruit or grapefruit products, Seville oranges (including marmalade containing Seville oranges) or star fruit within the 3-day period prior to the first venetoclax administration and until the last day of treatment is completed due to possible CYP3A mediated metabolic interaction.

Table 1. Excluded and Cautionary Medications

Excluded
Anticancer therapies including chemotherapy, radiotherapy, or other investigational therapy, including targeted small molecule agents: Excluded 5 half-lives prior to first dose and throughout venetoclax administration

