Biologic agents (e.g., monoclonal antibodies) for anti-neoplastic effect: Excluded 30 days prior to first dose and throughout venetoclax administration
Excluded during initiation and the dose-titration phase and Cautionary at 400 mg Steady Daily Dose:
Strong CYP3A inhibitors Exclude during initiation and the dose-titration phase. If subject requires use of these medications after the dose titration phase at steady daily 400 mg doses, use with caution and reduce the venetoclax dose by at least 75% during co-administration. Resume the venetoclax dose that was used prior to initiating the CYP3A inhibitor 2 to 3 days after discontinuation of the inhibitor
Cautionary
Moderate CYP3A inhibitors Avoid concomitant use of venetoclax with moderate CYP3A inhibitors at initiation and during the dose-titration phase. Consider alternative treatments. If a moderate CYP3A inhibitor must be used, reduce the initiation dose, titration doses and the 400 mg steady daily dose of venetoclax by at least 50%. Resume the venetoclax dose that was used prior to initiating the CYP3A inhibitor 2 to 3 days after discontinuation of the inhibitor.
Strong and Moderate CYP3A inducers Avoid concomitant use of venetoclax with strong or moderate CYP3A inducers. Consider alternative treatments with less CYP3A induction.
Warfarin
P-gp substrates
BCRP substrates
OATP1B1/1B3 substrates
P-gp inhibitors
BCRP inhibitors

Note: See [Appendix C](#) for Examples.

Table 2. Sample of Permitted Medications

Drug or Therapy	Comments
Colony stimulating factors e.g., G-CSF, GM-CSF	Permitted ; per ASCO guidelines. ³³ Notify AbbVie medical monitor if subject requires use of these medications or recombinant human erythropoietin.
Best supportive care and treatment e.g., antiemetics, antibiotics, transfusions, nutritional support, pain control, etc.	Permitted
Antih herpes and anti-pneumocystis prophylaxis	Permitted ; if clinically indicated.
Autoimmune thrombocytopenia and hemolytic anemia medications	Permitted ; if clinically indicated.

A sample list of excluded medications and cautionary medications that fall into these categories is provided in [Appendix C](#). It is not possible to produce a complete list of medications that fall into these categories, so if in question, please refer to the appropriate product label.

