A CT scan with contrast will be accepted if previously performed within 35 days prior to the first dose of venetoclax. Otherwise, a CT scan must be performed within the Screening window (28 days) for all subjects. A CT scan will be performed for all subjects at Week 48 to confirm disease response. Contrast-enhanced CT scans including neck, chest, abdomen, and pelvis will be performed to assess response to treatment. A contrast-enhanced MRI of the neck, chest, abdomen and pelvis with a non-contrast CT scan of the chest may be used for subjects in whom a contrast CT is medically contraindicated (i.e., subjects with a severe allergy to CT contrast agents or subjects with impaired renal clearance). Whichever method is used at Screening should be consistently used throughout the duration of the study.

Any CT scan (or MRI) performed as standard of care throughout the study should be captured on the eCRF.

NOTE: CT scans (or MRI) may be performed 7 days prior to the scheduled visit.

Bone Marrow Aspirate and Biopsy

At baseline, a bone marrow aspirate and biopsy are not required; however results should be recorded if available. If the subject achieves a CR by clinical criteria and confirmatory CT scan, a bone marrow aspirate and biopsy will be performed to confirm the CR. If a CT scan is performed and does not confirm a CR, a bone marrow biopsy should not be obtained.

Bone marrow aspirates and biopsies performed as standard of care throughout the study should also be captured on an eCRF.

Final Visit

Upon treatment discontinuation (Section 5.4.1), the reason(s) for discontinuation will be recorded in the eCRFs and a Final Visit will be performed. The Final Visit procedures as listed in [Appendix D](#) and [Appendix E](#) should be performed as soon as possible after study drug discontinuation.

At the Final Visit all used/unused study drug are to be returned to the site and drug accountability performed.

30-Day Safety Visit

A 30 day Safety Follow-up Visit should be performed approximately 30 days (\pm 3 days) following the last dose of venetoclax (to allow for AE collection 30 days following last dose of study drug). Refer to [Appendix D](#) and [Appendix E](#) for procedures to be performed.

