8.1.2.2 Secondary Endpoints

Secondary quality of life endpoints will include all multi-item scales and single-item scales from the EORTC QLQ-C30, EORTC QLQ-CLL16, and EQ-5D-5L. Scores will be calculated based on the scoring manual for each instrument.

Key secondary efficacy endpoints will include Complete Remission rate (CR + CRi), Overall Response Rate (ORR), Duration of Overall Response (DOR), Time to Progression (TTP), Duration of Progression-Free Survival (PFS) and Overall Survival (OS).

Complete remission rate (CR + CRi) defined as the proportion of subjects achieving a CR or CRi as their best response (per the investigator assessment) based on IWCLL NCI-WG criteria. In addition, the ninety-five percent (95%) confidence interval based on binomial distribution will be constructed for the calculated CR rate.

ORR will be assessed as the proportion of subjects with an overall response (CR + CRi + nPR + PR) based on the IWCLL NCI-WG criteria. The ninety-five percent (95%) confidence interval based on binomial distribution will be constructed for the calculated CR rate.

Duration of overall response will be defined as the number of days from the date of first response (CR, CRi, nPR, or PR) to the earliest recurrence or PD. If a subject is still responding, then the subject's data will be censored at the date of the subject's last available disease assessment. For subjects who never experience response, the subject's data will be censored on the date of enrollment. Duration of overall response will be analyzed by Kaplan-Meier methodology using data for all enrolled subjects. Median duration of overall response will be calculated and the corresponding 95% confidence interval will be presented.

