Time to progression (TTP) will be defined as the number of days from the date of first dose or enrollment if not dosed to the date of earliest disease progression. All disease progression will be included regardless whether the event occurred while the subject was taking the study drug or had previously discontinued the study drug. If the subject does not experience disease progression, then the data will be censored at the date of last available disease assessment. Data for subjects who receive non-protocol, CLL therapy prior to disease progression will be censored at the last disease assessment prior to receiving non-protocol therapy. Data for subjects without any disease assessments performed after the baseline visit will be censored at the time of enrollment plus 1 day. TTP will be analyzed by Kaplan-Meier methodology using data for all subjects enrolled. Median time TTP will be calculated and 95% confidence interval for median time TTP will be presented.

Progression-free survival (PFS) will be defined as the number of days from the date of first dose to the date of earliest disease progression or death. All disease progression will be included regardless whether the event occurred while the subject was taking the study drug or had previously discontinued the study drug. If the subject does not experience disease progression or death, then the data will be censored at the date of last disease

assessment. Data for subjects who receive non-protocol, CLL therapy prior to disease progression will be censored at the last disease assessment prior to receiving non-protocol therapy. Data for subjects without any disease assessments performed after the baseline visit will be censored at the time of enrollment plus 1 day. PFS will be analyzed by Kaplan-Meier methodology using data for all subjects enrolled. Median time PFS will be calculated and 95% confidence interval for median time PFS will be presented.

Overall survival (OS) will be defined as number of days from the date of first dose to the date of death for all dosed subjects. For subjects who did not die, their data will be censored at the date of last study visit or the last known date to be alive, whichever is later. OS will be analyzed by Kaplan-Meier methodology using data from all enrolled subjects. Median time survival will be estimated and 95% confidence interval for the median time survival will be presented.

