10.2 Quality of Life and Efficacy Analyses

Data collected at any point prior to the specified interim cutoff date during the study will be used in the analyses, unless otherwise specified. The population of these analyses is defined in Subsection [5.1.1](#).

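### ORR and CR+CRi use the best response at any time on study, with no cut at non-protocol CLL therapy, so a response to a later regimen can count as a venetoclax response

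*SAP*

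**What the plan says.** **Response rates.** SAP 10.1.2 defines CR+CRi and ORR as proportions of subjects "as assessed by investigator using the best response at any time during the study". SAP 10.2.2 adds the exact confidence interval but no limit on the window. SAP 10.2 sets the general data rule: "Data collected at any point prior to the specified interim cutoff date during the study will be used in the analyses". Protocol 8.1.2.2 describes the complete remission rate as the proportion "achieving a CR or CRi as their best response (per the investigator assessment) based on IWCLL NCI-WG criteria", also without a cut at other therapy.

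**TTP and PFS.** For these two endpoints Protocol 8.1.2.2 does set a cut: subjects "who receive non-protocol, CLL therapy prior to disease progression will be censored at the last disease assessment" before that therapy. The TTP and PFS definitions in SAP 10.1.2 do not repeat it.

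**Time on study after venetoclax.** Protocol 5.3.1.1 and 5.4.1 provide two years of follow-up calls after venetoclax stops, with subsequent cancer therapies recorded. Protocol 13.0 runs the study to the last visit or last follow-up contact.

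**Response data.** Protocol 5.3.1.1 specifies the Week 48 response assessment and CT for all subjects, with no on-treatment condition. It adds: "Any CT scan (or MRI) performed as standard of care throughout the study should be captured on the eCRF". A parallel sentence covers bone marrow samples.

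**The concern.** The objective in Protocol 4.0 and SAP 4.1 is the response to venetoclax monotherapy. A subject who stops venetoclax without a response, starts another CLL regimen and then has a remission recorded before the data cutoff meets the SAP definition of a responder. That subject also enters the DOR analysis, timed from a response that venetoclax did not produce.

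At stake are the two response rates, the complete remission rate in BCRi-treated subjects (a secondary objective in its own right), the subgroup forest plots of SAP 10.3, and DOR. The primary quality-of-life endpoint is not affected.

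**Working it through.** **1. The plan's own figure.** The documents size the study only on the change in GHS/QoL; ORR and CR+CRi have no sizing figure. With SD 20.5, a difference of 5, one-sided alpha 0.025 and 90% power (SAP 4.3), n = (20.5 × (1.960 + 1.282) / 5)² = 176.6, so 177, as stated. This does not depend on the response window, so neither the problem nor the fix changes 177 or 200.

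**2. Is the missing cut supplied elsewhere?**

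| Endpoint | Cut at non-protocol CLL therapy: protocol | SAP |
|---|---|---|
| CR+CRi | none | none |
| ORR | none | none |
| DOR | none | none |
| TTP, PFS | yes (8.1.2.2) | not carried over |

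No general rule in SAP 6.0 or 10.2 fills the gap.

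**3. Direction.** A best-response rule takes the most favourable category in the window. Extending the window past the start of another therapy can turn a non-responder into a responder, never the reverse. The rates can therefore only move up.

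**4. Size.** If k of the x counted responders first responded after other CLL therapy, the corrected rate is (x − k)/200, and each case is worth 1/200 = 0.5 points. The documents do not give k. The starting rates below are assumptions, set near the venetoclax monotherapy figures in Protocol 3.0 (CR+CRi 11.7% and 32.1%; ORR 75.0% and 81.7%). The values of k only show scale. Intervals are Clopper-Pearson 95%.

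| Counted as written (k = 0) | k = 2 | k = 5 | k = 10 |
|---|---|---|---|
| CR+CRi 23/200 = 11.5% (7.4–16.8) | 10.5% (6.6–15.6) | 9.0% (5.4–13.9) | 6.5% (3.5–10.9) |
| CR+CRi 64/200 = 32.0% (25.6–38.9) | 31.0% (24.7–37.9) | 29.5% (23.3–36.3) | 27.0% (21.0–33.7) |
| ORR 150/200 = 75.0% (68.4–80.8) | 74.0% (67.3–79.9) | 72.5% (65.8–78.6) | 70.0% (63.1–76.3) |
| ORR 163/200 = 81.5% (75.4–86.6) | 80.5% (74.3–85.8) | 79.0% (72.7–84.4) | 76.5% (70.0–82.2) |

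The size of the prior-BCRi subgroup is not given. One case there is worth 100/n points: 1 point if n were 100, 2 points if n were 50 (both assumed).

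**5. DOR.** SAP 10.1.2 computes DOR as the event date minus the earliest response date plus 1, with the earliest progression as the event. Suppose a subject progresses at Week 36 and first responds, on another regimen, at Week 48. With the nominal days in SAP Table 2 (246 and 330), DOR = 246 − 330 + 1 = −83 days. The formula presumes that response precedes progression, but the response window does not ensure it. This is why the cut should include progression as well as new therapy.

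**The case against.** The strongest reply is that the route is narrow, and that stands.

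- Response needs an investigator assessment against the IWCLL criteria. These are scheduled only at Weeks 24, 36 and 48, with optional confirmation of CR up to Week 108 for Week 48 partial responders. A routine-care scan alone is not a response; CR also needs blood counts, examination, absence of symptoms and a marrow.
- Appendix D has no disease assessment, CT or marrow at the final visit, the 30-day visit or in post-treatment follow-up. That follow-up is by telephone and does not list response to later therapy among its items.
- Other anticancer therapy is excluded while venetoclax is given.
- The analysis cutoff is tied to the last subject's Week 48 (Protocol 8.1.3), so many subjects would contribute little or no post-treatment time. A reader might infer that two full years of off-drug response data enter the rates; the cutoff and the schedule do not support that.

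A reader might also infer a second route during venetoclax, through drugs given for autoimmune cytopenia. The support is weak. Protocol 5.2.3 says "limited corticosteroid treatment is allowed while on study for significant active autoimmune cytopenias", and its Table 2 row "Autoimmune thrombocytopenia and hemolytic anemia medications" is conditional on clinical need, not unlimited. Anti-neoplastic use of steroids and biologics is barred. In the protocol's background, steroids appear only combined with alemtuzumab, and ofatumumab alone gave a 4.7% response rate with no complete responses in the 17p-deleted cohort. Ending the window at any steroid course could also misclassify true responders: a short course before Week 24, the first scheduled assessment, would make a later venetoclax remission uncountable.

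Finally, these are secondary, descriptive endpoints with no hypothesis test. That limits the consequence, but the rates would still be reported as those of venetoclax monotherapy.

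**Conclusion.** The point holds as a defect in a stated rule. Followed literally, SAP 10.1.2 credits venetoclax with a response reached on a later CLL regimen, and nothing in either document prevents it. The protocol already treats such therapy as a reason to stop counting for TTP and PFS, so the response rates are out of step with its own approach.

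The direction is certain for ORR and CR+CRi; the size is unknown. Each case is worth 0.5 points at N = 200 and proportionally more in the prior-BCRi subgroup. The relative effect is greatest for CR+CRi if that rate is low. A reader might infer that the rates are materially inflated. The documents do not support this: they give no count of affected subjects, the values of k above are illustrative, and the limits on the route suggest a small number, possibly none.

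**What to change.** In SAP 10.1.2 and 10.2.2:

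1. Count only responses assessed before the earlier of disease progression or the start of any non-protocol CLL therapy.
2. Treat subjects with no response by then as non-responders, and keep them in the denominator.
3. Start DOR only from a response that meets rule 1.
4. Do not end response counting at corticosteroids given for other indications. At most, add a sensitivity analysis of ORR and CR+CRi that leaves out responses first recorded after systemic corticosteroids for autoimmune cytopenia.

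While editing, either carry the protocol's TTP and PFS censoring rule into the SAP or justify leaving it out. Separately, the Table 2 row and the text of Protocol 5.2.3 on autoimmune cytopenia medications should be reconciled; the response-rate point does not depend on that.

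The cost is a few lines of SAP text and one derived date from therapy records already collected, provided start dates are recorded. There are no new visits and no change to the sample size. The downside is that reported rates may fall slightly.

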4.5 Timing of Quality of life and Efficacy Analyses and Safety Evaluations

Table 1. Summary of Analyses with Cutoff Dates and Data Included

Reason	Database Version	Cutoff Date	QoL/Efficacy Data Included	Safety Data Included
DMC	A	24 Apr 2017	Not included	All safety data ^a
DMC	F	03 Nov 2017	Not included	All safety data ^a
DMC	G	30 Apr 2018	Included	All safety data ^a

a. Safety population is defined in Section 5.1.1.

Quality of life, efficacy, and safety analysis occur when all subjects participating in the study have completed the 48-week disease assessment or have discontinued venetoclax (including early termination of the study). Quality of life, efficacy, and safety data up to the cutoff date specified in Table 1 will be considered. During this data collection period, active subjects continue to receive venetoclax, as applicable. When data collection is complete and all data management quality assurance (QA) and quality control (QC) procedures are performed, the clinical database data should be extracted for documentation and statistical analyses. The study will be considered completed when the last enrolled subject discontinues or completes the dosing regimen.

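### SAP 10.1.2 counts progression whenever found, but its censoring dates are undefined (TTP, DOR), not tied to a progression check (PFS), or missing (non-protocol CLL therapy)

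*SAP*

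**What the plan says.** **Events (SAP 10.1.2).** For TTP: "All PD will be included regardless of whether the event occurred while the subject was taking venetoclax or had previously discontinued venetoclax". PFS has the same rule plus death. DOR counts radiographic or clinical progression, or death, with no time limit.

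**Censoring (SAP 10.1.2).**
- TTP: "If the subject does not experience PD, then the subject's data will be censored at the date of the last available disease evaluation". With nothing after baseline: "If a subject does not have any post baseline disease assessments, the data will be censored at the first dose date plus 1 day".
- DOR: "If a subject is still responding then the subject's data will be censored at the date of the last available disease evaluation".
- PFS: censoring at the "date of the last available disease evaluation, last known alive date, or at the cut-off date for the interim analysis", with no rule for choosing between the first two. The no-data case reads "If a subject does not have any post baseline tumor assessment or clinical assessment for progression".
- OS: here the SAP does define its date. "The date of the last study visit will be determined by selecting the last available date of the following study procedures for a subject", and a list of procedures follows.

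**Missing-data rule (SAP 6.4).** Subjects with a missing progression date are treated as censored for TTP and PFS, at the interim data cutoff. DOR is not mentioned.

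**Protocol 8.1.2.2.** TTP and PFS non-progressors are censored at the last disease assessment. Subjects who start non-protocol CLL therapy before progression are censored at the last disease assessment before that therapy. SAP 10.1.2 has no counterpart to the second rule, and the protocol has none for DOR.

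**Schedule (protocol 5.3.1.1, Appendix D).** After baseline, Disease Assessments fall at Weeks 24, 36 and 48. Physical examination and hematology continue every 12 weeks to Week 108. After treatment stops, 6-monthly calls collect progression and survival for 2 years.

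**The concern.** A Kaplan-Meier curve is valid only if subjects leave the risk set for reasons unrelated to their outcome. Progression can be recorded at any later visit, work-up or call. If non-progressors are censored only at a formal assessment, those who stay well after Week 48 leave the risk set near that date while later progressors stay in it. PFS has the opposite fault: a subject known to be alive but not examined for progression still adds progression-free time. Without the non-protocol-therapy rule, progression after a new treatment counts against venetoclax, contrary to the protocol.

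At stake are the Kaplan-Meier medians and 95% confidence intervals for TTP, DOR and PFS, and the DOR and PFS plots by 17p, TP53 and prior BCRi status (SAP 10.3). Two programmers working from the same SAP could report different curves. The primary endpoint, ORR, CR rate and OS do not use these rules.

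**Working it through.** **Inputs.** The documents give no TTP, DOR or PFS figure to reproduce; the 177 subjects in the sample-size section concern quality of life. Nominal days come from SAP Table 2: Week 24 = Day 162, Week 36 = Day 246, Week 48 = Day 330, Week 108 = Day 750. Everything else is assumed: exponential times, the true medians, accrual, drop-out and frequency of late evaluations.

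**1. Mechanism.** Take 200 subjects: 20 progress before Week 48, 20 progress at Day 500, and 160 never progress.
- Non-progressors censored at Day 330: KM(500) = 0.90 × (1 − 20/20) = 0.
- Non-progressors censored at Day 750: KM(500) = 0.90 × (1 − 20/180) = 0.80.

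**2. Narrow reading (scheduled assessments only), cutoff at the last subject's Week 48.** A subject's follow-up ends at C, uniform on Day 330 to 330 + A, where A is the accrual period. For t > 330:

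KM(t) = S(330) × E[(S(t) − S(C))⁺] / E[S(330) − S(C)].

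With a true median of 730 days, h = ln 2/730 and S(330) = 0.731.
- A = 365: the denominator is 0.731 − 0.618 = 0.113. At t = 388 the numerator is 0.077, so KM = 0.731 × 0.077/0.113 ≈ 0.50. Estimated median about 390 days; 18-month estimate about 10% against a true 59%.
- A = 548: the denominator is 0.731 − 0.570 = 0.161. At t = 412 the numerator is 0.110, so KM ≈ 0.50. Estimated median 412 days (413 by simulation); 18-month estimate 23% against 59%.

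Shorter medians move little. With every subject followed for progression to Day 750, a true median of 365 gives 349 and a true 274 stays at 274.

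**3. Three readings of the same data.** Simulation with N = 200, two-year progression-free probability 70%, 10% drop-out by Week 48, 540-day accrual and cutoff at the last subject's Week 48. Progression-free at Week 84, true value 0.752:

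| Censoring date for non-progressors | Estimate |
|---|---|
| Last of Weeks 24/36/48 | 0.167 |
| Last 12-weekly visit | 0.751 |
| Data cutoff (SAP 6.4) | 0.773 |

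If 10%, 30% or 50% of non-progressors happen to have a later evaluation, the first row becomes 0.412, 0.596 or 0.681.

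**4. Before Week 48.** Subjects who stop drug early are still followed for progression, but on the narrow reading those who do not progress are censored at Week 36, Week 24 or first dose plus 1 day. With a true median of 730 and 10-30% stopping uniformly before Week 48, the estimate at Day 330 is 0.721-0.700 against 0.731.

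**5. DOR.** The distortion starts sooner on the DOR time scale: a Week 24 responder is censored at 330 − 162 + 1 = 169 days and a Week 48 responder at Day 1. Assume 150 responders, first response at Weeks 24/36/48 in 60/25/15%, true one-year DOR 75%, and follow-up to Week 108. The narrow reading gives 0.436 at one year; last-visit censoring gives 0.767.

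**6. PFS and the last-alive date.** Let a fraction q have no progression check after Day 330 but be known alive to Day 750, and let deaths be 20% of PFS events:

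PFS(t) = S(330) × [(1 − q)·exp(−h(t − 330)) + q·exp(−0.2h(t − 330))], with h = ln 2/730.

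- 18 months (Day 548): 0.605 for q = 0.1 and 0.616 for q = 0.2, against 0.594.
- Day 750: 0.509 and 0.527, against 0.491.

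**7. Non-protocol therapy.** The documents give no rate of switching before progression, so no size can be attached. The finding is the textual mismatch.

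**The case against.** The strongest reply is that the narrow reading is not the natural one. SAP 10.1.2 accepts clinical progression, and its PFS text speaks of clinical assessment for progression. Treatment continues only while the investigator sees no progression. SAP 3.0 says that it implements Amendments 1 and 2; protocol Appendix I shows that, before the current amendment, every physical examination covered nodes, liver and spleen. Under that text each 12-weekly visit supplied the clinical parts of a disease evaluation. This stands. A reader might infer that the plan as written biases TTP and DOR downward, but the documents do not settle that. The broad reading is at least as natural, and SAP 6.4 can be read to push the other way.

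The reply does not remove the ambiguity. The TTP paragraph itself switches to disease assessments. SAP 4.5 refers to subjects who have "completed the 48-week disease assessment or have discontinued venetoclax". Appendix D has a Disease Assessment row, separate from Physical Examination, marked after baseline only at Weeks 24, 36 and 48, both before and after the amendment.

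A second reply is that follow-up of every subject to Day 750 is unrealistic. This also stands: the only cutoff in SAP Table 1 that includes efficacy data, 30 April 2018, is 726 days after the original protocol date of 4 May 2016. Results that need follow-up to Day 750 are therefore illustrations only. The earlier cutoff does not remove the bias, as step 2 shows.

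A third reply is that a later visit helps only if progression status was recorded there. Under the current protocol a symptom-directed examination need not include nodes, and the documents show no field for progression-free status at those visits. This stands as a condition on the fix.

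**Conclusion.** The event and censoring rules for TTP, DOR and PFS are inconsistent and should be repaired. Two faults hold on any reading. The last-alive date biases PFS upward, by about 1-2 points at 18 months and 2-4 points at Day 750 if 10-20% of subjects go unchecked after Week 48 and deaths are 20% of events. The protocol's censoring before non-protocol CLL therapy has been dropped, with an effect that cannot be sized.

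The third fault is the undefined evaluation. Its bias is conditional: large and downward if only the scheduled assessments count and the true median is well beyond Week 48, largely absent if the 12-weekly visits count, and modestly upward if SAP 6.4 governs. A reader might also infer that estimates up to Week 48 are safe on any reading. They are not quite: on the narrow reading early discontinuers pull the Day 330 estimate down by 1-3 points, and DOR is affected earlier on its own time scale.

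All sizes rest on the assumed exponential times, medians, accrual and follow-up. No hypothesis test depends on these endpoints.

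**What to change.** Change the SAP wording:

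1. In 10.1.2, for TTP, DOR and PFS, define a disease evaluation as any visit or contact, scheduled or not, at which progression status was ascertained and recorded. Censor event-free subjects at the last such date on or before the cutoff.
2. Remove the last-alive date from the PFS censoring rule.
3. For TTP and PFS, restore the protocol 8.1.2.2 censoring before non-protocol CLL therapy, using the date defined in item 1. All progression up to the cutoff then counts, except progression after such therapy.
4. State that 6.4 does not override 10.1.2 for subjects with no known progression.

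**Cost.** One derived date, and no change to any protocol endpoint. Progression status must be available from the later visits and calls. Where it was not recorded, the visit does not count and the subject is censored earlier; a call that yields only vital status does not qualify. If such records are sparse after Week 48, some of the narrow-reading bias will remain and the report should say so.
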